2.4 Overview of Sample Size Considerations

2.4.1 Group A

A two-sided type I error rate is targeted at the pre-specified overall alpha level of 5% for the two primary analysis comparisons in Group A. To preserve the overall type I error rate in Group A and to allow flexible interim monitoring, a Bonferroni correction is applied, and a two-sided type I error rate of 2.5% each for the non-inferiority comparison between Arm 1 and Arm 3 and for the superiority comparison between Arm 2 and Arm 3 is allocated.

The sample size of N=187 per arm was derived as follows.

1. Non-inferiority comparison between Arms 1 and 3: For the primary objective to show that SPR proportion in Arm 1 is non-inferior to the SPR proportion in Arm 3 within the non-inferiority margin of 10%, we assume that 70% in the control arm (Arm 3) will achieve SPR. We assume the proportion of participants achieving SPR with two doses of HEPLISAV-B (Arm 1) will be higher at 75%. As a non-inferiority design, this comparison is powered to show that the SPR proportion in Arm 1 is not lower than that of Arm 3 (control) by more than the pre-specified non-inferiority margin of 10%. A sample size of 168 each in Arm 1 and Arm 3 achieves 80% power to detect a difference between the two proportions of less than 10%, in a one-sided test with type I error of 1.25% using

Page 7 of 25

normal approximation. Assuming no more than about 10% missing data for SPR, which includes loss to follow-up within each study arm prior to the primary outcome visit, the sample size is increased to 187 per study arm.

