2. Superiority comparison between Arms 2 and 3: For the primary objective to compare SPR proportions between Arm 2 and Arm 3 (control), an increase of 15% is assumed in the proportion of participants achieving SPR with three doses of HEPLISAV-B (Arm 2). With the sample size of 147 participants in each study arm, there is 80% power to detect a difference as significant in a two-sided test at a significance level of 2.5% using normal approximation. Formal interim efficacy analyses are planned for the Arm 2 and Arm 3 comparison, should the study enrollment allow such interim analyses to be useful to affect the conduct of the study. Assuming no more than three interim analyses for the study and applying the O'Brien and Fleming approach to preserve the two-sided type I error rate at 2.5%, Arm 2 and Arm 3 sample sizes should be at least 149 per study arm. Assuming no more than about 10% loss in the SPR data within each study arm, the targeted study sample size is 166 each for Arm 2 and Arm 3 to retain 80% power. To maintain 1:1:1 randomization across Arms 1, 2, and 3 throughout enrollment, the sample size in Arm 2 is increased to 187. Therefore, the power for the comparison between Arm 2 and Arm 3 is higher than 80%.

2.4.2 **Group B**

The study is powered to conclude that the proportion achieving SPR is greater than 55%. Assuming a response proportion of 75%, a sample size of 65 would provide at least 90% power in a two-sided test using normal approximation at a targeted significance level of 5%. Assuming at most 10% missing data, including loss to follow-up prior to the primary outcome visit, the study sample size is increased to 73.

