- For the secondary objectives on the analysis of the antibody titer as a continuous measure, two-sided type I error rate of 5% without correction for multiple analyses will be used. The geometric mean titer will be calculated for each analysis group (study arm or combined study arms, depending on the objective) and compared using a t-test. A two-sided 95% confidence interval around the difference in the geometric means will be calculated assuming t-distribution of log₁₀-transformed antibody titer. The confidence intervals will be provided across stratification factors and within stratum.
- o For the secondary objective (e.g. Objective 6) where Arms 1 and 2 are combined to compare to Arm 3 (control), the analysis will occur if the directions in the outcome differences between Arm 1 and Arm 3 and between Arm 2 and Arm 3 are the same. Otherwise, the analysis where Arms 1 and 2 are combined will not be interpretable.
- To address the objective on post-injection AEs, the proportion of participants with events will be summarized with a two-sided 95% confidence interval in each study arm using the Wilson method.
- Logistic regression models will be developed to assess host characteristic factors
 associated with vaccine response defined by the primary outcome on the SPR. The
 factors include age, sex, race, diabetes, body mass index (BMI), CD4+ T-cell count, and
 smoking status at baseline. Each factor will be considered in a separate model that only

controls for the study arm as a covariate, and a p-value <0.20 will determine entry into a full model. Then all-subsets variable selection approach will be used with a p-value cutoff of 0.05 as a criterion to retain in the final model, while keeping the study arm in the model throughout the procedure.

5.2.3 Group B Primary:

- The primary outcome on the SPR at 4 weeks after the vaccination series will be assessed by estimating the proportion of participants who achieve SPR. A two-sided 95% confidence interval around the observed SPR proportion will be provided using the Wilson score method for binomial variables. If the confidence interval lies above 55%, then it will be concluded that the SPR proportion is greater than 55%.
- To address the primary objective on safety, the proportion of participants with AEs will be summarized with a two-sided 95% confidence interval using the Wilson method.

5.2.4 Group B Secondary:

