- a. Secondary Objectives 1, 2, 3, 4, 5, 6, and 9 from Section 2.3.2 related to GMT will be addressed by estimating the difference in GMT between study arms (or between Arm 3 and the combined Arms 1 and 2 for Secondary Objective 6), using the approach described in Section 5.2.2. In addition, the geometric mean titer will be calculated for each study arm and compared using a t-test, as described in Section 5.2.2.
- b. Secondary Objectives 3, 4, 5 and 6 from Section 2.3.2 related to SPR will be addressed by estimating the SPR proportion differences between study arms (or between Arm 3 and the combined Arms 1 and 2 for Secondary Objective 6), using the approach described in Section 5.2.2.
- c. Secondary Objective 7 from Section 2.3.2 will be addressed by estimating the proportion of participants with post-injection AEs, using the approach described in Section 5.2.2. In addition, descriptive tables summarizing the events and the number of participants experiencing the events will be provided.
- d. Secondary Objective 8 from Section 2.3.2 will be addressed by logistic regression models described in Section 5.2.2.
- e. To assess the effect of sex and race on the vaccine response (per NIH guidance on reporting analyses of sex and racial differences in intervention effects for NIH-defined Phase III clinical trials), proportions of subgroups defined by sex and race who achieve the primary outcome will be estimated with confidence intervals, using the approach described in Section 5.2.2. In addition, note that logistic regression models for the primary outcome will include sex and race, and reported as secondary analyses.

Group B Outcomes Described in Section 3.2.2:

a. Secondary Objectives 1, 2 and 3 from Section 2.3.2 related to GMT will be addressed by estimating the GMT, using the approach described in Section 5.2.4.

- b. Secondary Objectives 2 and 3 from Section 2.3.2 related to SPR will be addressed by estimating the SPR proportion, using the approach described in Section 5.2.4.
- c. Secondary Objective 7 from Section 2.3.2 will be addressed by estimating the proportion of participants with post-injection AEs, using the approach described in Section 5.2.4. In addition, descriptive tables summarizing the events and the number of participants experiencing the events will be provided..

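### Group A host-factor odds ratios are reported only for factors that pass significance filters; one pre-specified model showing all seven factors would give unselected estimates

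*SAP*

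**What the plan says.** Secondary Objective 8 for Group A (SAP Section 2.3.2) is to assess which host characteristics are associated with vaccine response. Section 5.2.2 gives the method, a logistic regression on the primary SPR outcome:

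- The candidates are seven baseline variables: smoking, CD4+ count, BMI, diabetes, race, sex and age.
- Each is fitted separately, adjusted for arm only; at this step "a p-value <0.20 will determine entry into a full model".
- The second step searches over subsets of the factors that got through: "Then all-subsets variable selection approach will be used with a p-value cutoff of 0.05 as a criterion to retain in the final model". Arm is never removed.

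The SAP describes no shrinkage, no bootstrap, no selection-adjusted interval and no report of the unselected multivariable model. Section 5.2.4 applies the same approach to Group B. Section 6, item 11(e), on sex and race differences, asks the reader to "note that logistic regression models for the primary outcome will include sex and race". The Group B list under item 11 repeats that statement.

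**The concern.** The objective is an estimation question: how strongly is each characteristic related to seroprotection? Under Section 5.2.2 a multivariable odds ratio is reported only if its own p-value is below 0.05 in the selected model. Estimates that pass such a filter are on average further from the null than the truth. Standard intervals around them ignore the filtering. A factor that just misses the cutoff gets no multivariable estimate, so readers cannot tell an imprecise result from evidence of little association.

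Selection is usually defended on the ground that there are too few outcomes for all the candidates. The question is whether that applies at the planned Group A size.

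**Working it through.** **1. Evaluable sample size.** The inputs are in SAP Section 2.4.1: "we assume that 70% in the control arm (Arm 3) will achieve SPR"; the proportion with "two doses of HEPLISAV-B (Arm 1) will be higher at 75"%; and for Arm 2 "an increase of 15% is assumed in the proportion of participants achieving SPR", hence 85%. The non-inferiority margin is 10%, with one-sided alpha 1.25% and 80% power.

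n per arm = (2.2414 + 0.8416)² × (0.70×0.30 + 0.75×0.25) / (0.05 + 0.10)² = 9.505 × 0.3975 / 0.0225 = 167.9, so 168 as stated. Then 168/0.9 = 186.7, so 187 as stated. With 168 evaluable in each of three arms, N = 504.

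**2. Outcomes available, Group A.** Non-responders are the rarer outcome: 168 × (0.25 + 0.15 + 0.30) = 117.6.

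- Arm (2 df) plus seven single-df factors is 9 parameters: 117.6/9 = 13.1 each.
- With 12 parameters (assumed extra race and smoking categories): 117.6/12 = 9.8.
- If response were 90/90/80% (assumed): 168 × 0.40 = 67.2, or 7.5 per parameter with 9.
- If 97/99/80% (assumed): 168 × 0.24 = 40.3, or 4.5.

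**3. Outcomes available, Group B.** Section 2.4.2 gives 65 evaluable at 75% response: 65 × 0.25 = 16.25 non-responders, and 16.25/7 = 2.3 per factor.

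**4. Simulation of the SAP rule, Group A.** The run had 1,500 trials, N = 504 and the planned arm rates. The SAP does not give the effects, the factor correlation of 0.15, or the tie-break (best AIC among subsets in which every factor has p<0.05); these are assumptions.

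| True OR | Retained | Mean OR if retained | Coverage if retained | Full-model OR | Full-model coverage |
|---|---|---|---|---|---|
| 0.78 per SD | 62.1% | 0.73 | 96.1% | 0.77 | 94.7% |
| 1.28 per SD | 57.4% | 1.38 | 95.0% | 1.29 | 95.2% |
| 0.60 | 37.8% | 0.44 | 92.4% | 0.60 | 95.0% |
| 1.40 | 26.9% | 1.87 | 91.3% | 1.42 | 95.3% |
| 0.75 | 25.4% | 0.55 | 86.4% | 0.75 | 93.7% |
| 1.00 | 5.5% | 0.90 | 0% | 0.99 | 95.1% |
| 1.00 | 5.6% | 0.99 | 0% | 1.00 | 94.7% |

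Exaggeration is ln(mean retained OR)/ln(true OR). For the five non-null rows, in order, it is 1.26, 1.29, 1.61, 1.86 and 2.08. Weighted by retention frequency: (0.621×1.26 + 0.574×1.29 + 0.378×1.61 + 0.269×1.86 + 0.254×2.08) / 2.096 = 3.16/2.096 = 1.5.

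Pooled coverage is the sum of retention × coverage over the sum of retention: 1.957/2.207 = 89%.

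The full model converged in every trial.

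**5. Like-for-like comparison.** A further 1,500-trial run used independent factors, with log-odds of 0.15–0.4 on five and zero on two. Both methods were judged only on factors with p<0.05.

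| | SAP rule | Full model |
|---|---|---|
| Exaggeration | 1.50 | 1.51 |
| Coverage | 90.3% | 90.1% |

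Detection per factor agreed within 0.01. With all seven factors null, at least one had p<0.05 in 29.2% of trials under the SAP rule and 29.7% under the full model. Seven independent 5% tests would give 1 − 0.95⁷ = 30.2%.

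**6. Simulation, Group B (N = 65, the same assumed effects as step 4).** Pooled coverage of retained factors under the SAP rule was 0.306/0.535 = 57%. The seven-factor model failed to converge in 8% of trials.

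**The case against.** The strongest reply is that comparing retained factors under the SAP rule with all factors under the full model sets unlike against like. Step 5 bears this out: among significant factors the two methods behave the same. A reader might infer that the p<0.20 screen or the all-subsets search does special damage, or that the SAP rule produces more false associations. The results support neither inference. The harm comes from reporting only what is significant. The benefit of the full model is that the unselected estimates are shown as well.

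A reader might also infer that Section 6, item 11(e), contradicts Section 5.2.2, since the selection rule can drop sex and race. The text does not go that far. It speaks of models in the plural, and the single-factor candidate models do include sex and race; nothing says that the final model must. It is an ambiguity. Item 11(e) also provides SPR estimates by sex and race with intervals, whatever the regression keeps.

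Two further points stand. The objective is secondary, and no primary or key secondary estimand depends on it. Section 6 also defers detail to the Analysis Implementation Plan, which is not among the documents, and Section 5.2.2 does not say that single-factor results will be withheld. Those results are adjusted for arm only, however, so they do not replace multivariable estimates for dropped factors.

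**Conclusion.** The concern holds in a limited form. The Group A multivariable odds ratios would be conditional on significance. At the planned response rates and assumed modest effects they are exaggerated about 1.5-fold on the log-odds scale, with about 90% coverage of nominal 95% intervals. Reporting all seven factors from one model gives about 1.01-fold and 95%. Undercoverage is an average: marked for weak or null factors and absent for the two stronger continuous ones (95–96%).

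The sizes depend on the assumed effects, correlation and tie-break. The count of about 118 non-responders depends on the planning rates, and support for a seven-factor model weakens if response is well above plan. It does not extend to Group B at any plausible rate near the 75% assumed. The primary conclusions do not depend on this analysis.

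**What to change.** - **Section 5.2.2 (Group A).** Replace the screen and the all-subsets search with one pre-specified logistic model: study arm, age, sex, race, diabetes, BMI, CD4+ count and smoking. Report the odds ratios of all seven factors with 95% intervals whatever their p-values. Keep the arm-adjusted single-factor models as descriptive.
- **Fallback.** State in advance that penalised estimation will be used in Group A if non-responders are far fewer than planned.
- **Section 5.2.4 (Group B).** Remove the cross-reference to the Group A approach, which would otherwise carry seven factors into about 16 non-responders. Report descriptive single-factor estimates only.
- **Section 6, item 11.** Say which models include sex and race: in Group A the pre-specified model, which settles the ambiguity in 11(e); in Group B the single-factor models.

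The cost is SAP wording, with less programming than all-subsets selection. The downside is a longer table that includes factors with no clear association. A note under the table should say that picking out the significant rows brings the exaggeration back and that the false-positive rate is unchanged.

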2.1.2 Group B (Vaccine-Naïve, N=73)

Group B study is designed as a single-arm study.

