- Each secondary analysis will be conducted using a two-sided type I error rate of 5% without correction for multiple analyses.
- To address the secondary objectives on the SPR at additional study weeks, a two-sided 95% confidence interval around the observed SPR proportion will be provided for each, using the Wilson score method for binomial variables.
- To address the secondary objectives related to antibody titer as a continuous measure, the GMT will be calculated with two-sided 95% confidence intervals, assuming tdistribution of log₁₀-transformed antibody titer.
- To address the study objective on post-injection AEs, the proportion of participants with events will be summarized with a two-sided 95% confidence interval using the Wilson method.
- Logistic regression models will be developed to assess host characteristic factors associated with vaccine response defined by the primary outcome on the SPR. The approach described for Group A (Section 5.2.2 above) will also be used for Group B.

References:

Yan, X., & Su, X. G. (2010). Stratified Wilson and Newcombe confidence intervals for multiple binomial proportions. Statistics in Biopharmaceutical Research, 2(3), 329-335.

Mantel, N., and Haenszel, W. (1959). "Statistical Aspects of Analysis of Data from Retrospective Studies of Disease." Journal of the National Cancer Institute 22:719–748.

6 Report Contents

Additional details will be provided in an AIP. In addition to results for primary and secondary outcome measures, baseline characteristics and study status are reported to ClinicalTrials.gov.

- 1. CONSORT Diagram
- 2. Study history
 - a. A summary of changes to and clarifications of the protocol
 - b. A brief summary of the DSMB reviews
- Study entry
 - a. Screening: Number of participants screened for the study
 - b. Accrual: Tables of accrual by month and by site
- 4. Baseline characteristics
 - a. Demographics: age, sex, gender, IV drug use, race, ethnicity, country
 - b. Weight and BMI
 - c. Plasma HIV-1 RNA level, CD4+ and CD8+ T-cell count and percent
 - d. ARV regimen
 - e. Smoking status
 - f. Diabetes status
- 5. Study status
 - a. Listing of premature study discontinuation with reasons. For premature discontinuations, the number of weeks on study will be provided.
- 6. Study treatment status

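### Group B takes over Group A's seven-factor selection procedure with about 16 expected non-responders, so selected weak or moderate associations will be overstated and sparse factors have no separation rule

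*SAP*

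**What the plan says.** SAP 5.2.2 sets out the host-factor analysis for Group A. The outcome is the primary seroprotection response (SPR). The candidates are age, sex, race, diabetes, BMI, CD4+ count and smoking. Each is fitted in its own logistic model with study arm as the only covariate, and p<0.20 admits it to a fuller model. All-subsets selection follows with a 0.05 cutoff, "while keeping the study arm in the model throughout the procedure".

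SAP 5.2.4 carries this to Group B in one sentence: "The approach described for Group A (Section 5.2.2 above) will also be used for Group B". The same section sets a two-sided 5% level for Group B secondary analyses, with no multiplicity correction.

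Group B is a single arm of 73 (SAP 2.1.2). SAP 2.4.2 gives the planning basis: "Assuming a response proportion of 75%, a sample size of 65 would provide at least 90% power in a two-sided test", and then "Assuming at most 10% missing data, including loss to follow-up prior to the primary outcome visit, the study sample size is increased to 73".

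The Group B part of SAP Section 6, item 11, adds that the logistic models will include sex and race. It labels the objectives 7 and 8, although SAP 2.3.2 lists only five for Group B.

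The SAP names no test for the p-values, no penalised or exact method, no rule for separation or sparse categories, and no exploratory label for these models. It leaves further detail to an Analysis Implementation Plan (AIP) that is not among the documents.

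**The concern.** The information in a logistic model is governed by the smaller outcome class, here the non-responders. Group A should have well over a hundred; Group B should have about 16. A data-driven search over seven factors on so few events keeps mainly the factors whose estimates happen to be large. The odds ratios that reach the report are then biased away from 1. A factor with few cases may also have none among the non-responders, in which case maximum likelihood gives no finite estimate.

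The study-arm instruction has no meaning in a single-arm group, which suggests that the text was carried over without adaptation.

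At stake is Group B Secondary Objective 5, host characteristics associated with response. SAP 1.1 places the SAP's primary and secondary outcome measures in the primary manuscript, so readers could take a short list of large odds ratios at face value.

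**Working it through.** **1. Reproduce the plan's figures.** Inputs from SAP 2.4.2: null 55%, alternative 75%, two-sided 5%, 90% power. With the null variance, n = (1.960 + 1.282)² × 0.55 × 0.45 / 0.20² = 65.0. With 10% missing, 65 / 0.90 = 72.2, rounded up to 73. Both figures agree with the SAP.

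**2. Expected non-responders.** 65 × 0.25 = 16.25, and 16.25 / 7 = 2.3 per candidate. If all 73 are evaluable, 73 × 0.25 = 18.25, or 2.6 per candidate. The 95% binomial range at n = 65 is 10 to 23. At other response rates with n = 65 the expected count is 29 (55%), 13 (80%) and 6.5 (90%). For Group A, 168 evaluable per arm at 75%, 85% and 70% gives 168 × (0.25 + 0.15 + 0.30) = 117.6.

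**3. How large an estimate must be to survive.** For a factor scaled to SD 1, SE ≈ 1/√(65 × 0.25 × 0.75) = 0.286. Reaching p<0.05 therefore needs an estimated OR of about exp(1.96 × 0.286) = 1.75 per SD. For a binary factor with prevalence q, divide the SE by √(q(1−q)): the threshold is about 3.1 at 50% and 6.5 at 10%. If the true log-OR per SD were 0.15, a retained estimate would have to be at least about 0.56 / 0.15 = 3.7 times too large.

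**4. Simulated selection.** The procedure was run on 1,500 samples per Group B scenario and 500 at n = 504. The following assumptions are not in the documents: independent factors; age, BMI and CD4+ standard normal; race binary; prevalences of sex 45%, race 40%, diabetes 10% and smoking 25%; Wald tests.

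| n, SPR | True OR | Kept in | Median OR when kept | Log-OR ratio to truth |
|---|---|---|---|---|
| 65, 75% | 1.5 per SD | 24% | 2.35 | 2.2 |
| 65, 75% | 2.0 binary | 19% | 5.5 | 2.6 |
| 65, 75% | 2.5 per SD | 77% | 3.0 | 1.3 |
| 65, 75% | 4 binary | 49% | 7.8 | 1.6 |
| 65, 75% | 3.5 per SD | 91% | 3.95 | 1.2 |
| 65, 75% | 6 binary | 66% | 9.5 | 1.3 |
| 504, 76.7% | 1.5 per SD | 96% | 1.51 | 1.05 |
| 504, 76.7% | 2.0 binary | 88% | 2.10 | 1.09 |

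A separate run with weak effects gave about 3.5-fold; another, with log-odds effects of 0.15 to 0.4, gave 4.4-fold. The weak-effect figure depends most on what is assumed.

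**5. Separation.** With no true association, the chance of no diabetic non-responder is (1 − 0.25 × prevalence)^65: 19% at 10% prevalence and 44% at 5%. At 90% SPR and 10% prevalence it is 52%.

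Take 49 responders, 6 of them diabetic, and 16 non-responders, none diabetic. The likelihood-ratio statistic is 3.59 (p ≈ 0.06), so diabetes passes the 0.20 screen with an infinite OR. The Wald p-value is near 1, so diabetes is dropped.

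With the same 49/16 split, three diabetic responders are enough to pass the likelihood-ratio screen (1.74, p ≈ 0.19) and two are not (1.15, p ≈ 0.28). Given no diabetic non-responder, the chance of three or more diabetic responders is about 0.885 at 10% prevalence and 0.45 at 5%. The chance that diabetes enters separated is then roughly 0.193 × 0.885 = 17%, or 0.44 × 0.45 = 20%.

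Simulated rates for the screened model at 75% SPR were about 0% under Wald tests. Under likelihood-ratio tests they were 18% to 45%, and 13% in a separate run.

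**The case against.** The strongest reply is that this is one secondary objective of Group B. It is not among the key secondary estimands in SAP 4.5, no efficacy or safety conclusion rests on it, and the unseen AIP may add detail. That limits the importance of the point. The SAP is nevertheless the document that prescribes the procedure, and it prescribes it without limits.

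A reader might infer that any factor reported for Group B will be grossly exaggerated, or that the model cannot be fitted. The documents do not support that:

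- Inflation for strong true effects is modest (1.2- to 1.6-fold).
- The model with all seven factors was not estimable in about 21% of runs at 75% SPR (50% at 5% diabetes prevalence, 62% to 66% at 90% SPR). But the SAP fits only the factors that pass the screen, and under Wald tests that model was almost never affected (0.2% or less).
- Even under likelihood-ratio tests, passing the screen is not retention at 0.05. In the 49/16 example, a separated diabetes term would need seven diabetic responders (p ≈ 0.04).

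Nor does the rate of chance findings show a small-sample fault. With no true associations, about 24% of runs at n = 65 kept at least one factor, against 32% at n = 504. This mostly reflects uncorrected testing of seven factors, which the SAP openly adopts. Seven single-factor Firth analyses still gave at least one p<0.05 in 21% of runs.

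It would also be one-sided to say that everything worsens with a better response. Separation and inflation do, but under Wald tests the rate of naming a null factor fell to about 17% at 90% SPR. The leftover arm term is harmless in itself: it is a constant and drops out.

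The fix is one of several. Fewer candidates or a penalised multivariable model would also answer the concern.

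**Conclusion.** The point holds as a worthwhile correction to a secondary analysis. About 16 expected non-responders for seven candidates follows from the SAP's own figures; it is an expectation at 75% SPR, not a fixed count. Selection on that count is unstable. Moderate true factors are kept in only about a fifth to a quarter of runs, with log-odds ratios more than doubled, whereas at Group A's size the same procedure inflates by 5% to 9%.

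Separation of a sparse factor is a material risk, but its consequence turns on a test that the SAP does not name. Under Wald tests the factor silently disappears; under likelihood-ratio tests it can enter with an infinite odds ratio. The hand calculation supports roughly 17% to 20% for diabetes under a likelihood-ratio screen with no true association. The upper end of the simulated range depends on further assumptions.

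All inflation and separation figures rest on assumed prevalences, effects and independence of factors. The Group B primary SPR conclusion is unaffected.

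**What to change.** In SAP 5.2.4, replace the cross-reference with a Group B method: report all seven prespecified single-factor associations with the primary SPR outcome, each by Firth penalised logistic regression with a 95% interval. Use no p-value screening, no multivariable selection and no study-arm term, and label the results descriptive.

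In simulation, this gave 96% to 97% interval coverage for null to moderate effects, and finite estimates under separation.

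In SAP Section 6, item 11, align the Group B statement that the models will include sex and race, since each would now have its own model. Correct the Group B objective numbers there from 7 and 8 to 4 and 5.

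The cost is SAP wording. Group B would have no confounder-adjusted model, which about 16 events could not support reliably. Chance findings from seven uncorrected analyses remain, so the results should be read as estimates with intervals and not as a list of significant factors.
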